#### **Parameters with NCI-CTC grades available:**

The laboratory toxicities will be tabulated using descriptive statistics (number of patients and percentages) during the on-treatment period. The denominator to calculate percentages for each laboratory parameter is the number of patients evaluable for CTCAE grading (ie those patients for whom a Grade 0, 1, 2, 3 or 4 can be derived).

- The summary of laboratory parameters by CTCAE grade table will include number and percentage of patients with Grade 1, 2, 3, 4, Grade 3/4 and any grade (Grades 1-4), laboratory abnormalities during the on-treatment period.
- The shift table will summarize baseline CTCAE grade versus the worst on-treatment CTCAE grade. The highest CTCAE grade during the on-treatment period is considered as the worst grade for the summary.
- The number and percentage of patients with newly occurring or worsening laboratory abnormalities during the on-treatment period will be summarized by worst grade on-treatment (Grade 1, 2, 3, 4, Grade 3/4 and any grade (Grades 1-4)).

The above analyses apply to hematology and chemistry evaluations which can be graded per CTCAE, ie:

- Hematology:  
Hemoglobin (HB), Leukocytes (white blood cell decreased), Lymphocytes (lymphocyte count increased/decreased), Neutrophils / Absolute Neutrophils Count (ANC) (neutrophil count decreased), Platelet Count (PLT) (platelet count decreased).
- Serum Chemistry:  
Albumin (hypoalbuminemia), Alkaline Phosphatase (alkaline phosphatase increased), Alanine Aminotransferase (ALT) (ALT increased), Amylase (serum amylase increased), Aspartate Aminotransferase (AST) (AST increased), Total Bilirubin (blood bilirubin increased), Cholesterol (cholesterol high), Creatinine (creatinine increased), Creatine Kinase (CPK increased), Potassium (hypokalemia/ hyperkalemia), Sodium (hyponatremia/ hypernatremia), Magnesium (hypomagnesemia/hypermagnesemia), Calcium (hypocalcemia/ hypercalcemia), Glucose (hypoglycemia/hyperglycemia), Gamma Glutamyl Transferase (GGT) (GGT increased), Lipase (lipase increased), Phosphates (hypophosphatemia), Triglycerides (hypertriglyceridemia)

In addition, hematology and chemistry laboratory parameters by CTCAE grade (any grade and Grade  $\geq 3$ ) will also be summarized by treatment phase. Laboratory tests will be included in the summary for each treatment phase if the laboratory test date/time occurs anytime from first dose date/time of study treatment in the treatment phase through minimum(first dose date/time of study treatment in next treatment phase, end of on-treatment period).

#### **Parameters with NCI-CTC grades not available:**

Hematology and chemistry evaluations which cannot be graded per CTCAE criteria will be summarized as frequency (number and percentage) of patients with:

- shifts from baseline normal to at least one result above normal during on-treatment period
- shifts from baseline normal to at least one result below normal during on-treatment period

In this study, these apply to the following parameters:

- Hematology: Absolute Monocytes, Absolute Eosinophils, Absolute Basophils
- Serum Chemistry: Chloride, Total Urea, Uric Acid, Total Protein, C-Reactive Protein, Lactate Dehydrogenase (LDH)

#### **6.6.5.2. Other laboratory parameters**

All other parameters collected on the eCRF will be listed in dedicated listings presenting all corresponding collected information on the eCRF.

- Coagulation: activated partial thromboplastin time (aPTT) and prothrombin time (INR).
- Urinalysis: protein, glucose, blood
- Thyroid function tests: TSH, free T4

- Other parameters: adrenocorticotrophic hormone (ACTH)
- Pregnancy test

The listings of laboratory results will be provided for all laboratory parameters. The listings will be sorted by parameters and assessment dates or visits for each patient. Laboratory values that are outside the normal range will also be flagged in the data listings, along with corresponding normal ranges. A listing of CTCAE grading will also be generated for those laboratory tests.

In addition, listings of abnormal values will be provided for hematology, chemistry, urinalysis, coagulation parameters. If there is at least one abnormal assessment for any parameter, all the data for that laboratory parameter will be included into the listing.

For all tests not mentioned above but present in the clinical data, a listing of patients with at least one result for the relevant test will be provided.

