8.	Blood Chemistry (core panel): Core chemistry panel is required on Day 1 of the Lead-in Phase; and Days 1, 8, 22, 25, 39, and 43 of the CRT Phase. Core panel must be performed, and results reviewed by the treating physician prior to study drug administration. When an infusion is shifted towards another day, chemistry panel will be shifted accordingly; additional assessments whenever clinically indicated.
9.	Thyroid Function and ACTH Tests: Free T4, TSH, and ACTH tests will be performed at Screening and every 8 weeks thereafter. Additional tests should be performed when clinically indicated.
10.	Serum/Urine Pregnancy Test: For patients of childbearing potential, a serum or urine pregnancy test, with sensitivity of at least 25 mIU/mL, will be performed on two occasions prior to starting study treatment: once at the start of screening and once on the Day 1 of the Lead-in Phase immediately before avelumab/placebo administration. Additional pregnancy tests (serum or urine) will also be routinely repeated prior to avelumab/placebo dosing during the CRT Phase and Maintenance Phases. In addition, pregnancy tests will be performed whenever one menstrual cycle is missed or when potential pregnancy is otherwise suspected. Additional pregnancy tests may also be undertaken if requested by Institutional Review Board (IRB)/Ethics Committees (ECs) or if required by local regulations. Results of the pregnancy test should be evaluable prior to each dosing.
11.	Urinalysis: Required only at Screening. To be performed as clinically indicated at other time points.

12. **12-Lead Electrocardiogram (ECG):** All patients require a single ECG measurement at screening. Triplicate ECGs will be collected in at least 30 patients in each treatment arm. In these patients, on-treatment triplicate ECGs will be performed on the day of avelumab/placebo administration (ie, Day 1 of the Lead-in Phase, and Days 8, 25, and 39 of the CRT Phase; if the avelumab/placebo dosing day is shifted for patient scheduling reasons, the ECG assessment should be shifted also). At each time point, three (3) consecutive 12-lead ECGs (triplicates) will be performed approximately 2 minutes apart to determine mean QTc (average of triplicates) prior to avelumab/placebo administration and at the end of infusion. Additional single ECGs may be performed as clinically indicated. Clinically significant findings seen on ECGs during the treatment period should be recorded as adverse events.

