7.	Thyroid Function Tests: Free T4, TSH, and ACTH will be performed on Day 1 and then every 8 weeks thereafter during the Maintenance Phase, and at the End of Treatment/Withdrawal and 30-day Short Term Follow-up visits after the last administration of study treatment unless performed in the prior 8 weeks.
8.	Serum/Urine Pregnancy Test: For female patients of childbearing potential, a serum or urine pregnancy test, with sensitivity of at least 25 mIU/mL, will be performed prior to each avelumab/placebo administration during the Maintenance Phase, and at the End of Treatment/Withdrawal and 30-day Short Term Follow-up visits, and additionally whenever one menstrual cycle is missed or when potential pregnancy is otherwise suspected. Additional pregnancy tests may also be undertaken if requested by Institutional Review Board (IRB)/Ethics Committees (ECs) or if required by local regulations.
9.	Urinalysis: Required only at the End Of Treatment/Withdrawal. To be performed as clinically indicated at other time points.
10.	12-Lead Electrocardiogram (ECG): Additional single ECG measurements may be performed as clinically indicated. For End of Treatment/Withdrawal, a single ECG measurement will be obtained for all patients. Clinically significant findings seen on ECGs should be recorded as adverse events.

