Immune-related adverse events (irAEs): in the pooled safety data (N=1738), a total of 247 patients (14.2%) experienced irAEs, defined as adverse events requiring use of corticosteroids (and/or hormonal therapy for endocrinopathies), and no clear alternate etiology. The median time to first onset of an irAE was 11.7 weeks. The most frequent irAEs were thyroid disorders including hypothyroidism (5.2%), hyperthyroidism (0.4%) and thyroiditis (0.2%), immune-related rash (5.2%), immune-related colitis (1.5%), immune-related pneumonitis (1.2%), immune-related hepatitis (0.9%), adrenal insufficiency (0.5%) and immune-related myositis (0.5%). In addition, irAEs reported in 0.1% of patients in the pooled safety dataset included: type 1 diabetes mellitus, immune-related nephritis/renal dysfunction, hypopituitarism, uveitis and Guillain-Barre Syndrome. The majority of irAEs were Grade 1 or Grade 2 in severity, with 39 (2.2%) being of Grade  $\geq 3$  severity. Fatal outcome was reported in 1 patient (0.1%) with immune-related pneumonitis, and 2 patients (0.1%) with immune-related hepatitis. Other relevant irAEs reported with avelumab outside

the pooled safety dataset included 1 case of fatal immune-related myocarditis in Study B9991002 (avelumab in combination with axitinib for renal cell carcinoma (RCC)), 1 case of non-fatal immune-related myocarditis in the 20 mg/kg cohort of the dose escalation phase of Study EMR100070-001, and 2 patients with non-fatal graft versus host disease (GVHD) in Study B9991007 (avelumab in patients with classical Hodgkin's lymphoma).

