### **5.5.2.4. Concurrent Radiation Therapy Adverse Events**

Grade 3 or 4 (CTCAE v4.03) therapy-induced mucositis and/or dysphagia, which are enhanced by cisplatin, are expected to develop in about two thirds of patients. Nutritional evaluation prior to the initiation of therapy for a prophylactic percutaneous endoscopic gastrostomy (PEG) tube placement is highly recommended. Placement of a feeding tube should be recorded, as should use of a feeding tube during and after treatment (eg, greater than or less than 50% of nutrition by tube). Other common radiation adverse events include: fatigue, weight loss, regional alopecia, xerostomia, hoarseness, transient ear discomfort, dysgeusia, and skin erythema and desquamation within the treatment fields.

Less common long-term treatment adverse events include: hypothyroidism, loss of hearing, chronic swallowing dysfunction requiring permanent feeding tube, and cervical fibrosis.

Much less common radiation adverse events include: mandibular osteoradionecrosis (<5% incidence), and cervical myelopathy (<1% with restriction of spinal cord dose to ≤45 Gy).

Treatment interruptions are allowed if there is symptomatic mucositis or skin reaction that, in the judgment of the clinician, warrants a break. For chemotherapy-attributable AEs requiring a break in treatment, IMRT may continue if clinically appropriate.

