### **9.5.2. Laboratory Abnormalities**

Laboratory test results will be graded according to the NCI CTCAE v4.03 severity grade. The frequency of patients with laboratory test abnormalities will be summarized according to the worst grade for each laboratory test.

For laboratory tests without an NCI CTCAE grade definition, results will be categorized as normal (within normal ranges), abnormal, or not done.

Shift tables will be provided to examine the distribution of laboratory abnormalities.

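### The SAP only lists TSH, free T4 and ACTH, with no by-arm summary, although Protocol 9.5.2 promises categorisation and shift tables for ungraded laboratory tests

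*SAP*

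**What the plan says.** **Testing.** Footnote 9 to Protocol Table 2 states: "Free T4, TSH, and ACTH tests will be performed at Screening and every 8 weeks thereafter". Footnote 7 to Protocol Table 3 continues: "Free T4, TSH, and ACTH will be performed on Day 1 and then every 8 weeks thereafter during the Maintenance Phase". It adds the end-of-treatment and 30-day visits unless the tests were done in the previous 8 weeks. All three tests are among the required tests in Protocol Table 12.

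**Protocol analysis.** Protocol 9.5.2 states: "For laboratory tests without an NCI CTCAE grade definition, results will be categorized as normal (within normal ranges), abnormal, or not done". It also promises shift tables for laboratory abnormalities. Thyroid tests and ACTH are not exempted.

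**SAP summaries.** For tests without a CTCAE grade, SAP 6.6.5.1 counts patients who were normal at baseline and had at least one on-treatment result above normal, and likewise below normal. It then names the tests covered: monocytes, eosinophils, basophils, chloride, urea, uric acid, total protein, C-reactive protein and LDH.

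**SAP listings.** SAP 6.6.5.2 opens with "All other parameters collected on the eCRF will be listed in dedicated listings presenting all corresponding collected information on the eCRF" and places "Thyroid function tests: TSH, free T4" in that group, followed by ACTH. Listings for all laboratory parameters will flag out-of-range values beside the normal ranges. The additional abnormal-value listings are for hematology, chemistry, urinalysis and coagulation only.

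**The concern.** Protocol 1.2.2 puts thyroid disorders first among the most frequent immune-related events with avelumab. Both arms also receive radiation to the primary lesion and neck, and Protocol 5.5.2.4 says of it: "Less common long-term treatment adverse events include: hypothyroidism, loss of hearing". Some thyroid change can therefore be expected in the control arm, and the useful safety question is how much avelumab adds. That is a between-arm question, and patient listings do not answer it. The SAP would report by-arm shifts for chloride and uric acid but not for TSH or free T4.

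At stake is the completeness of the safety description: laboratory change that never became a reported or treated event would not be counted by arm.

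**Working it through.** There is no design figure to reproduce for the gap itself. The check sets the texts side by side, with three small sums.

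**1. Where the three tests go in the SAP**
- CTCAE-graded list (6.6.5.1): TSH, free T4 and ACTH are absent, so the SAP itself treats them as ungraded.
- Ungraded tests with shift counts (6.6.5.1): absent from the nine named tests.
- Listing-only group (6.6.5.2): all three present.
- Abnormal-value listings (6.6.5.2): their categories are not named.

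The other members of the listing-only group are coagulation, urinalysis and pregnancy tests. Coagulation and urinalysis are mostly done when clinically indicated. The thyroid panel is repeated on a schedule, so a summary over time is feasible.

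**2. Is the thyroid group the most frequent?** Protocol 1.2.2 gives 247 of 1738 patients with an immune-related event: 247/1738 = 14.2%, as stated. Thyroid disorders: 5.2% + 0.4% + 0.2% = 5.8% if the categories do not overlap, against 5.2% for rash. The protocol's ordering is supported. This rationale applies to TSH and free T4. ACTH is an adrenal/pituitary test.

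**3. How much data is involved?**
- Screening: 1.
- Lead-in and CRT: 7 + 63 = 70 days, or 10 weeks. Screening may be up to 4 weeks before randomization. Maintenance thus starts about 10 to 14 weeks after screening, which leaves room for 1 test at the 8-week interval.
- Maintenance: weeks 0, 8, 16, 24, 32, 40 and 48, so 7.
- Total: 1 + 1 + 7 = 9 per completer, and 9 × 640 = 5,760 results per test. This is an upper figure, because not all patients will complete. The end-of-treatment and 30-day tests are left out because they are waived if done in the previous 8 weeks.

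**4. Do the adverse-event tables replace the missing summary?**
- Protocol 8.5 makes an abnormal result reportable if it brings symptoms, further testing or intervention, a dosing change or discontinuation, or significant added treatment, or if the investigator or sponsor judges it an adverse event. An asymptomatic, untreated TSH shift may meet none of these.
- SAP Appendix 1, Table 24 counts an immune-related event only if it was treated (steps 3 and 4). Step 5 then removes it if the site records a clear other cause, unless pathology confirms an immune mechanism.

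Both outputs describe events. Neither gives a by-arm count of measured change.

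**The case against.** Several points on the other side are sound.

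- **The data are not discarded.** They are listed in full with out-of-range flags, which partly meets the categorisation in Protocol 9.5.2. A listing still gives no count by arm and no shift table.
- **Thyroid harm is compared by arm.** SAP 6.6.1.1 tabulates treatment-emergent events by preferred term and worst grade. SAP 6.6.4 tabulates immune-related events by cluster and gives risk differences with 95% CIs. A reader might infer that the arms are never compared on thyroid effects. That is wrong: the gap is in measured values only.
- **Attribution is blinded.** A reader might infer that sites will blame neck irradiation and so bias the immune-related count between arms. The documents do not show this. The trial is double-blind, Protocol 5.2 has possible immune events treated as if the patient were on avelumab, step 5 needs a clear other cause, and medical review may add cases the algorithm missed. Protocol 5.5.2.4 also classes radiation hypothyroidism as less common and long-term, while on-treatment summaries stop at most 30 days after the last dose.
- **The SAP may depart from the protocol.** Both documents allow this without an amendment unless the change is a major one to the primary endpoint or its analysis. The SAP version history records an update to the listed laboratory parameters but gives no reason for listing these tests only.
- **The SAP has a general low/normal/high rule.** It could be read to cover thyroid tests, but it sits under the hematology and chemistry heading. The closed list there and the explicit placement in 6.6.5.2 exclude that reading.
- **Other documents are not available here.** The Safety Review Plan and the separate SAP for the data monitoring committee might contain thyroid summaries. That cannot be checked, and nothing in the protocol or this SAP says so.

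**Conclusion.** The point stands as a gap in descriptive safety reporting and a mismatch between Protocol 9.5.2 and SAP 6.6.5. Followed as written, the SAP yields no by-arm count of measured TSH, free T4 or ACTH change, although up to about 5,760 results per test would be collected if every patient completed treatment. Untreated or unreported biochemical change is the part that goes uncounted. How many patients that is cannot be said, because the documents give no rate of abnormal TSH.

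A reader might go further and ask for powered comparisons, risk differences or composite laboratory categories. The documents do not support that: the SAP calls its safety analyses exploratory and plans risk differences for adverse events, not for any laboratory parameter. The primary analysis is unaffected.

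The conclusion assumes that the named list in SAP 6.6.5.1 is closed and that no other document supplies the summary. For ACTH the case is consistency with Protocol 9.5.2 alone.

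**What to change.** Add TSH and free T4 to the SAP 6.6.5.1 list of ungraded parameters, and add ACTH for consistency with Protocol 9.5.2. Report, by arm, n (%) of patients with normal baseline values who shift above normal and who shift below normal on treatment. A split by treatment phase is optional. The listings in SAP 6.6.5.2 can stay. If the sponsor prefers listings only, the SAP should say why it departs from Protocol 9.5.2.

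The cost is a line of SAP wording and one descriptive table from data already collected. Visits, tests and patient management do not change.

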#### **6.6.6. Vital signs**

Weight for the purposes of dose calculation will be recorded at screening and within 3 days pre-dose Day 1 of each cycle. Weight will not be collected at End of Treatment. Height will be measured at screening only.

Vital sign summaries will include all vital sign assessments from the on-treatment period. All vital sign assessments will be listed, and those collected outside the on-treatment period will be flagged in the listing.

All vital sign parameters will be summarized using descriptive statistics (mean, SD, median, Q1, Q3, minimum, and maximum) of actual values and changes from baseline for each visit over time. End of Treatment visit will be summarized separately. The changes computed will be the differences from baseline.

#### **6.6.7. Electrocardiogram**

ECG summaries will include all ECG assessments from the on-treatment period. All ECG assessments will be listed, and those collected outside the on-treatment period will be flagged in the listing. QTcB and QTcF will be derived based on RR and QT (see below). When triplicates are collected (for approximately 30 subjects in each treatment arm), the average of the replicate measurements should be determined after the derivation of the individual parameter at each time point.

#### **Selecting Primary QT Correction for Heart Rate**

The analysis of QT data is complicated by the fact that the QT interval is highly correlated with heart rate. Because of this correlation, formulas are routinely used to obtain a corrected value, denoted QTc, which is independent of heart rate. This QTc interval is intended to represent the QT interval at a standardized heart rate. Several correction formulas have been proposed in the literature. For this analysis we will use some of those methods of correction,

as described below. The QT interval corrected for heart rate by the Bazett's formula, QTcB, is defined as

$$QTcB = \frac{QT}{\sqrt{RR}},$$

the QT interval corrected for heart rate by the Fridericia's formula, QTcF, is defined as

$$QTcF = \frac{QT}{\sqrt[3]{RR}},$$

where RR represents the RR interval of the ECG, in seconds, and can be estimated as 60/Heart Rate.

Although Bazett's correction is the historical standard, it does not perform well when heart rate fluctuates. Fridericia's formula may perform better under these conditions.

### ECG Summaries

The following analyses will be performed for each applicable ECG parameters (RR, PR, QRS, QT, ventricular rate –denoted as HR in what follows-, and QTc) by treatment arm, during the on-treatment period. The denominator to calculate percentages for each category is the number of patients evaluable for the category.

- Pearson correlation between QT and HR, QTc (QTcB, QTcF) and HR using individual (non-averaged) baseline assessments
- For each of the ECG parameters (HR, and QT, QTc, QRS, PR intervals), descriptive statistics at baseline, at each post-baseline time point and changes from baseline at each post-baseline time point
- Frequency (number and percentage) of patients with notable ECG values according to the following categories:
  - QT/QTc increase from baseline >30 ms, >60 ms;
  - QT/QTc > 450 ms, > 480 ms, > 500 ms;
  - HR ≤ 50 bpm and decrease from baseline ≥ 20 bpm;
  - HR ≥ 120 bpm and increase from baseline ≥ 20 bpm;
  - PR ≥ 220 ms and increase from baseline ≥ 20 ms;
  - QRS ≥ 120 ms.

Patients with notable ECG interval values and qualitative ECG abnormalities will be listed for each patient and time point and the corresponding notable values and abnormality findings will be included in the listings.

Unscheduled ECG measurements will not be used in computing the descriptive statistics for change from baseline at each post-baseline time point. However, they will be used in the analysis of notable ECG changes and the shift table analysis of notable QT parameters.

